While there is significant evidence for the safety and efficacy of direct penicillin challenge in the evaluation of penicillin allergy, this has not yet been widely implemented in the primary care setting. There have been two pilot studies exploring direct amoxicillin challenge in the pediatric primary care setting. The first was a retrospective study of 42 children in Australia who included children greater than 18 months old. They performed direct amoxicillin challenges after 3 months had elapsed from the index reaction. There was a 3% positive challenge rate and all reactions resolved with only oral diphenhydramine. The second was a prospective study that included 102 children in Ireland and there were no positive challenges to amoxicillin challenge. This approach has not been studied in the United States. A recent survey of US-based pediatricians identified perceived barriers to implementing penicillin allergy evaluations into their routine care (17). Significant gaps in knowledge exist regarding the feasibility of this approach involving direct amoxicillin challenge procedures in low-risk patients in the pediatric primary care setting.

4. Joint Task Force on Practice P, American Academy of Allergy A, Immunology, American College of Allergy A, Immunology, Joint Council of Allergy A, et al. Drug allergy: an updated practice parameter. *Ann Allergy Asthma Immunol.* 2010;105(4):259-73.
6. American Academy of Allergy Asthma and Immunology Report on the Allergy and Immunology Physician Workforce (1999-2009/10). Rensselaer, NY: The Center for Health Workforce Studies; 2012 [Available from: <https://www.aaaai.org/Aaaaai/media/MediaLibrary/PDF%20Documents/Practice%20and%20Parameters/2012-AI- Physician-Workforce-Report.pdf>].

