Currently there is no standard protocol in the Children's Health pediatric primary care clinic for evaluation of penicillin-allergy labels. Most often, children with a penicillin allergy label are referred to the Children's Health pediatric allergy clinic for evaluation of penicillin allergy regardless of their risk status based on the history of their index reaction to penicillin.

3. Study Design.

Describe the study design (e.g., single/double blind, parallel, crossover, etc.) Consider inserting a scheme to visually present the study design.

This study is a prospective, descriptive, single arm study of a convenience sample of children from age 2-18 with a history of parent reported penicillin allergy who present to an outpatient pediatric clinic for a routine healthcare maintenance visit.

4. Research Plan / Description of the Research Methods:

4.a. Provide a comprehensive narrative describing the research methods.

- 1) Provide the **order in which tests/procedures will be performed**,
- 2) Provide the **setting** for these events and a description of the **methods used to protect privacy** during the study.
- 3) Provide the **plan for data analysis** (include as applicable the **sample size calculation**)

Please respond to all components of this item, or clearly indicate which components are not applicable.

Patients will be recruited from the pediatric primary care clinic at the Children's Health Specialty Center Dallas campus who are scheduled for a routine healthcare maintenance visit, have a penicillin allergy listed in the electronic medical record, and have consented to participate in research activities. Patient caregivers will receive a telephone call, where in a study member will introduce the topic of penicillin allergy and delabeling through direct

amoxicillin challenge and obtain verbal consent to administer a risk-stratifying questionnaire evaluating the index reaction and their interest in proceeding with the amoxicillin challenge, including reasons for hesitancy and perceived barriers. Subjects with a history of reactions consistent with severe cutaneous adverse reactions will be excluded. The study member will review the oral amoxicillin challenge procedure and assess caregiver and patient's interest in proceeding with oral amoxicillin challenge.

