A single dose of amoxicillin 50 mg will be administered at the start of the healthcare maintenance visit. Subjects will be observed for 10 minutes and if no reaction, will be given a second 200 mg dose and observed for a further 50 minutes for immediate reactions, defined as onset of urticaria, angioedema, cough, wheezing, rhinitis, repetitive vomiting, diarrhea, protracted abdominal pain, or hypotension, and managed accordingly. This direct amoxicillin challenge testing is the recommended evaluation for low-risk patients, and the investigatory component of this study is if it can be performed in conjunction with a routine healthcare maintenance visit in the pediatric primary care setting. During this observation period, subjects will have their healthcare maintenance visit with the primary pediatric provider. Subjects who have a negative oral challenge will be provided documentation of their immediate tolerance of penicillin. Upon completion of challenge, a survey will be administered to families to assess the quality of their experience and identify areas for improvement. If immunizations are indicated per the CDC vaccination schedule, they will be administered after this 60-minute period of observation from the challenge. Subjects will be discharged with instructions to contact the pediatrician and study team for any delayed symptoms. We will also measure the duration of each subject's time in the clinic from check in to check out. A follow up encounter will occur over the phone at 7-10 days after the date of oral challenge to assess for delayed reactions. At 1 year post-challenge, subjects' penicillin allergy status will be assessed in the electronic medical record, and patients who have had penicillin allergy label added back to their allergy list will be contacted via telephone to assess reasons for the

addition of the penicillin allergy label. Descriptive statistics will be used to describe the population completing amoxicillin challenge testing.

4.b. List of the study intervention(s) being tested or evaluated under this protocol			
 N/A - this study does not test or evaluate an intervention. Skip to item 4.d.			

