All groups/subjects	One benefit will be the accurate diagnosis of current penicillin tolerance status. If penicillin tolerant, would have the benefit of using penicillin-based antibiotic treatment for future infections and diminishing the harms associated with a penicillin-allergy label which include prolonged hospital stays, increased surgical site infections, increased rates of Clostridium Difficile infections, and increased healthcare utilization costs when compared to patients without a penicillin allergy label. Another benefit includes increased access to evaluation, as this evaluation would be included within patients' healthcare maintenance visit and not require a separate referral to an allergist with the associated barriers of time and cost with seeing another provider.

If you are requesting a Waiver of Informed Consent, complete the table below.

If you have a consent form, **list the reasonably foreseeable [risks](#) in the consent form (and do not complete this section).**

List the risks according to the probability (likely, less likely or rare) and magnitude (serious or not serious).

(include: 1) expected adverse events; 2) rare and serious adverse events; 3) all other psychological, social, legal harms)

Do not delete frequency. Frequency must be estimated because it will assist you with determining which adverse events will require prompt reporting.

	Not serious	Serious
Likely These risks are expected to occur in more than 20 out of 100 subjects.	•	•
Less likely These risks are expected to occur in 5-20 subjects or less out of 100 subjects.	•	•
		Serious

Rare These risks are expected to occur in less than 5 subjects out of 100		•	
--	--	---	--

4.c. Study Intervention #1 Insert name used in 4.b.	
List each group exposed to this intervention on a separate line. (e.g., experimental, control, Arm A, Arm B, etc)	For each group, list the benefits of this intervention. (Benefits can be directly from the intervention or from a monitoring procedure likely to contribute to the subject's well being). If there are no benefits, state "none".
Or state All Groups/Subjects	

If you are requesting a Waiver of Informed Consent, complete the table below.

If you have a consent form, list the reasonably foreseeable **risks** in the consent form (and do not complete this section).

List the risks according to the probability (likely, less likely or rare) and magnitude (serious or not serious).

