(include: 1) expected adverse events; 2) rare and serious adverse events; 3) all other psychological, social, legal harms)

Do not delete frequency. Frequency must be estimated because it will assist you with determining which adverse events will require prompt reporting.

	Not serious	Serious
Likely These risks are expected to occur in more than 20 out of 100 subjects.	•	•
Less likely These risks are expected to occur in 5-20 subjects or less out of 100 subjects.	•	•
		Serious
Rare These risks are expected to occur in less than 5 subjects out of 100		•

		
4.d. List ALL other research procedures or components not listed in table 4.b.
 
The combination of Tables 4b and 4d should account for all of the research procedures that will take place during this study.
 
Consider grouping similar procedures under a single component (e.g., blood work, CT = safety assessments)
		
#	Research component	Column A	Column B	Column D
	
 individual procedures 
example:
 
Eligibility Assessments
 
 History and physical Questionnaire Laboratory tests 
Add or delete rows as needed
	
Local Standard Practice Indicate the number of times each procedure will be performed as stipulated in the research plan that would be performed if the participant were not participating in the study.
	
Research Only
 
Indicate the number of times each procedure will be performed solely for research purposes (meaning that the participant would not undergo the same number of procedures or would not undergo the procedure(s) at the same frequency if they were not participating in the study)
	
Risks
 
If you are requesting a Waiver of Informed Consent, complete the table below.
 
List the reasonably expected risks for each procedure or group of procedures under the following categories as appropriate:
 
 • Serious and likely; • Serious and less likely; • Serious and rare; • Not serious and likely; • Not serious and less likely
1	Eligibility Assessments			
	Questionnaire assessing Index Reaction and hesitancy and barriers to pursuing challenge		1	Not Serious and Less Likely
2	Healthcare Maintenance Visit			
	History and Physical	1		Not Serious and Less Likely
	Insert procedure here			
	Insert procedure here			
3	Post-challenge Assessment			

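### Does the 1-year label check fail because section 4.a never says who removes the penicillin entry from the medical record, or when?

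*Combined protocol and SAP*

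**What the plan says.** Four places in the combined protocol bear on this point.

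- **Entry (section 4.a).** Recruited patients must "have a penicillin allergy listed in the electronic medical record", so every child starts with a label.
- **After a negative challenge (section 4.a).** The one stated action is: "Subjects who have a negative oral challenge will be provided documentation of their immediate tolerance of penicillin". The later call at 7-10 days asks about delayed reactions, and no action on the label is attached to it.
- **At 1 year (section 4.a).** Allergy status is read from the electronic record, and "patients who have had penicillin allergy label added back to their allergy list will be contacted via telephone" so that the reasons can be asked.
- **Analysis (section 4.a).** Descriptive statistics are planned for the children who complete the challenge. No relabeling rate, denominator or endpoint is defined.

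Section 1 gives the overall goal as the feasibility of delabeling in primary care. Its two specific aims are risk stratification and completion of the direct challenge. Section 4.a adds that the investigational question is whether the challenge can be done alongside a routine maintenance visit.

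**The concern.** The 1-year step presupposes an event that the narrative does not describe. The child arrives with a label, receives proof of tolerance, and a year later may have had the label put back. The removal in between is missing: no role, no contact, no recorded date.

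If some removals are missed, two different children show a label at 1 year without having reacted. One was never updated, which is a failure of implementation. The other was updated and later relabelled, perhaps by another provider. These have different causes. Read literally, the telephone rule reaches only the second child. The risk-benefit table in section 4.c counts "diminishing the harms associated with a penicillin-allergy label" among the benefits, and for a tolerant child much of that benefit depends on the entry coming off.

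Two further passages seem to strengthen the point. The instruction above table 4.d says: "The combination of Tables 4b and 4d should account for all of the research procedures that will take place during this study"; neither table lists an allergy-list update. Section 2.b says: "Currently there is no standard protocol in the Children's Health pediatric primary care clinic for evaluation of penicillin-allergy labels", which could suggest that routine practice would not supply the step.

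**Working it through.** The plan states no figure on this point, so there is none to reproduce. The check is mainly a comparison of texts, followed by a short calculation of possible size.

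**1. Is removal stated or only implied?** Section 4.a does not state it. The word delabeling and the reference to a label being put back both imply it. Giving a family proof of tolerance is not the same as editing the chart. The silence is confirmed, and so is the intent.

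**2. Do the procedure tables show that removal was left out of the study?** Hardly. Table 4.d also has no row naming the 1-year chart check, the 1-year call about reasons, the family experience survey or the measurement of clinic time, although section 4.a describes all four. Its only post-challenge row is a single questionnaire. A table this condensed says little about any one missing step. An allergy-list edit may also be ordinary charting rather than a research procedure; the documents do not say.

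**3. Does section 2.b show that the clinic would not update the list?** No. It concerns how labels are evaluated, and its next sentence concerns referral to the allergy clinic. It does not address how allergy lists are maintained after a test result.

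**4. Are the two kinds of child inseparable at 1 year?** Only if the electronic record keeps no history of allergy-list changes. The documents do not mention such a history either way. The plan does require staff to decide from the chart whether a label was put back, so they must look for evidence of re-entry.

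**5. How large could the confusion be?** Let p be the positive-challenge rate and u the share of negative-challenge children never updated. Then never-updated tolerant children per 100 challenged = 100 × (1 − p) × u.

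Inputs for p come from section 2. For the first primary care pilot: "There was a 3% positive challenge rate and all reactions resolved with only oral diphenhydramine". For the second: "there were no positive challenges to amoxicillin challenge". The top of the range across the cited studies is 13%. The values of u are assumptions.

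| p | u = 0 | u = 5% | u = 10% | u = 20% |
|---|---|---|---|---|
| 0% | 0 | 5.0 | 10.0 | 20.0 |
| 3% | 0 | 4.85 | 9.7 | 19.4 |
| 13% | 0 | 4.35 | 8.7 | 17.4 |

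Each entry is the assumed u, in per cent, multiplied by 0.87 to 1. The documented rates barely move it, so the table returns the assumption and is not evidence of a problem.

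**6. Would a stated result be biased?** If an analyst counted every label present at 1 year as a relabeling, the share among negative-challenge children would be (1 − r) + r × q, with r the share removed and q the true relabeling share. With q = 5% (assumed):

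- r = 100%: 0 + 0.05 = 5%
- r = 90%: 0.10 + 0.045 = 14.5%
- r = 80%: 0.20 + 0.04 = 24%

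That would be a serious misreading, but the plan does not set up such a count. It reads status and asks about labels that were put back.

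**The case for a change.** The strongest case for a change is that the form asks for a comprehensive narrative in the order of procedures, that the missing step is the one that gives delabeling its name, and that naming a role and keeping a date would cost a sentence or two and a data field. Dates are easier to record at the time than to reconstruct a year later, and a chart history that nobody has promised is a weak safeguard.

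Part of this stands. The text is silent, the step matters to the child, and in a record system without a change history a missed update could pass for a relabeling. The cost argument is also fair.

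It does not show that the plan would go wrong. A low price is not a reason for amendment when no stated aim or result depends on the step. More writing would not by itself meet the most practical complaint either: a removal date would separate the two groups, but as long as the telephone rule covers only labels put back, nobody would ask why an entry was never updated. Nor is chart removal the only route to benefit. Section 4.c also lists an accurate diagnosis and future use of penicillins, and families leave a negative challenge with proof of tolerance.

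**Conclusion.** No change follows. Section 4.a leaves out an operational detail that a team running a delabeling study would fill sensibly: after a tolerated challenge, someone updates the allergy list and the chart shows it. The timing of that update is a clinical matter for the study team, and the documents do not contradict themselves on it.

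The effect on the two specific aims and on the question of performing the challenge within a maintenance visit is nil. The effect on the descriptive 1-year status is unknown and may be zero. It exceeds zero only if some updates are missed, and it confuses the reading only if the record also shows no trace of whether an entry was removed. Neither condition can be judged from the documents.

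This conclusion rests on the 1-year check remaining descriptive, as it is now. The consent pages are not in the available text, so the point is confined to the sections cited.

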	Questionnaire assessing post-challenge status		1	Not Serious and Less Likely
	Insert procedure here			
	Insert procedure here			

4	Urine Pregnancy Test		1	Not Serious and Less Likely
	Insert procedure here			
	Insert procedure here			
	Insert procedure here			

5. Safety Precautions. (Describe safeguards to address the serious risks listed above.)

a. Describe the procedures for protecting against or minimizing any potential risks for each of the more than minimal risk research procedures listed above.

NA

b. Where appropriate, discuss provisions for ensuring necessary medical or professional intervention in the event of adverse events, or unanticipated problems involving subjects.

Risks of Protocol Specified Medications/Procedures

- Adverse reactions to amoxicillin include headache, diarrhea, nausea, vomiting, rash, and allergic reactions. Allergic reactions range from mild to severe, and if a patient has an allergic reaction, he/she may need oral, IM, or IV medications. The site investigators for this trial are credentialed advanced health providers who are trained to recognize and manage systemic reactions. Treatment will be available within 60 seconds in the event of a reaction. Emergency medications as listed below will be available to treat any allergic reactions.
- Treatment of individual acute allergic reactions during the conduct of the study may include antihistamines, epinephrine, β -adrenergic agonists, oxygen. The risks of these common medications include the following
 - o Antihistamines: drowsiness, dizziness, constipation, stomach upset, blurred vision, dry mouth/nose/throat
 - o Epinephrine: tachycardia, palpitations, nervousness, sweating, nausea, vomiting, trouble breathing, headache, dizziness, anxiety, tremors, pale skin
 - o β -adrenergic agonists: nervousness, shaking, headache, dizziness
 - o These risks will be minimized by appropriate dosing per guideline management of systemic allergic reactions.

c. Will the safeguards be different between/among groups?

Yes

No

If yes, describe here

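### Section 4.a names a telephone call as the only source of reasons for labels added back by 1 year; the record entry, already open at that step, should be abstracted as well

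*Combined protocol and SAP*

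**What the plan says.** Section 4.a of the combined protocol and SAP sets two linked steps at 1 year. The first uses the record: "At 1 year post-challenge, subjects' penicillin allergy status will be assessed in the electronic medical record". The second applies to children whose label has come back: "patients who have had penicillin allergy label added back to their allergy list will be contacted via telephone to assess reasons for the" addition. The call is the only source named for reasons.

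Follow-up before that is limited. After the challenge, "Subjects will be discharged with instructions to contact the pediatrician and study team for any delayed symptoms", and there is one scheduled contact: "A follow up encounter will occur over the phone at 7-10 days after the date of oral challenge to assess for delayed reactions". The stated analysis is one sentence: "Descriptive statistics will be used to describe the population completing amoxicillin challenge testing". It sets no categories for the reasons and no handling of children whose family is not reached.

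The procedures table in section 4.d, which together with table 4.b is meant to cover every research procedure, has one post-challenge line, "Questionnaire assessing post-challenge status". It has no line for the 1-year record check or the 1-year call.

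**The concern.** A returned label is an event in the record. Somebody entered it on some date, perhaps with a reaction described and perhaps linked to a visit or a prescription. The study team has that record open when it finds the label, yet the plan names only a later conversation as the way to learn why it is there. The caregiver may not have made or seen the entry and may be asked about it many months afterwards. A family that cannot be reached supplies nothing, and no fallback is stated.

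The reason matters for how the 1-year result is read. A label that returned after a new reaction to penicillin bears on the child's tolerance. A label re-entered with no new event bears on record keeping. The two call for different responses from a clinic adopting the procedure. The 1-year check is also the only planned measure of whether removed labels stay off. The benefit claimed in section 4.c, fewer of the harms linked to a penicillin label, depends on that.

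**Working it through.** The plan states no figure to reproduce: no sample size, expected re-labeling rate or contact rate. The check is therefore a reading of every mention of late follow-up, record review and telephone contact, set side by side.

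1. **Label status at 1 year.** Source: the electronic record (section 4.a).
2. **Reason for a returned label.** Source: a telephone call (section 4.a). No second source appears in section 4.a or in the tables in 4.b and 4.d.
3. **Delayed reactions to the study challenge.** Source: the call at 7-10 days, plus families' own reports to the pediatrician or study team (section 4.a). This covers one possible reason, close to the event. What a family tells the pediatrician may be charted, but the plan does not say those notes will be read.
4. **Events between the 7-10 day call and 1 year.** No scheduled contact. The 1-year step is the only planned opportunity to find a later exposure and reaction.
5. **Fallback, categories and rule for conflicting sources.** None stated.

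Two consequences follow from items 2 and 5. A child whose family is not reached has no reason recorded. A child whose family is reached has a reason that rests on recall over an interval of anything up to a year.

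The size of the first consequence can only be illustrated. Unknown reasons = number re-labeled × (1 − contact rate). With 10 re-labels and contact rates that are assumptions, not figures from the documents:

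| Assumed contact rate | Unknown reasons per 10 re-labels |
|---|---|
| 50% | 10 × 0.50 = 5 |
| 70% | 10 × 0.30 = 3 |
| 85% | 10 × 0.15 = 1.5 |

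The table restates the assumed contact rate. It does not estimate what this study will lose, or how many of those reasons the record would supply.

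**The case against.** The strongest reply is that this is a short institutional form for a feasibility study and need not list every field to be abstracted. The record is opened at the same step, and nothing forbids reading the entry. That is right. A reader might infer that the plan excludes the entry as evidence, but this would be drawn from silence. The same holds for the inference that only a snapshot is taken, so that a label added and removed within the year is missed. The wording covers children who have had the label added back and does not settle whether list history is read.

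A second reply is that the call is not a poor source. A caregiver can say whether the child took penicillin again and reacted, including outside this health system. An allergy entry may itself only repeat what a caregiver told staff. The documents do not describe what an entry contains or how complete it is. They therefore do not support calling the telephone the weaker source, or saying that new reactions cannot be told from clerical re-entry.

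A third reply is that no stated conclusion rests on the item. The objective in section 1 is risk stratification and completion of challenges in primary care, and section 3 describes the design thus: "This study is a prospective, descriptive, single arm study of a convenience sample of children from age 2-18". This also stands, and it limits the weight of the point.

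What remains is narrower. The plan chose to collect reasons, names one source that will be missing for some children, and leaves unnamed a second source that is already at hand.

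**Conclusion.** The point holds as an inexpensive improvement to a secondary descriptive item. Following section 4.a as written leaves the reason unknown for every family not reached, and otherwise relies on recall about an entry that the family may not have made. Using the record as well should reduce the unknowns. By how much cannot be calculated, because the documents give no number challenged, re-labeling rate, contact rate or measure of how complete the entries are.

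Three stronger conclusions are tempting and not supported:

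- **That a label returning after a later reaction shows the challenge failed.** The study documents immediate and current tolerance, and a reaction on a later exposure does not by itself contradict that.
- **That one or two misclassified reasons would change the study's conclusion.** No hypothesis, threshold or sample size is attached to re-labeling.
- **That chart review would leave almost nothing unknown.** Entries may be incomplete.

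The verdict assumes that the entry carries at least some usable detail, such as a date or a reaction field, and that the study team can retrieve it. The main feasibility objective is not affected.

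**What to change.** Amend section 4.a as follows.

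- For each label added back by 1 year, abstract from the record the date of entry, the role of the person entering it, the reaction text, and any linked encounter or penicillin order.
- Read the allergy-list history over the whole year where the record makes it available.
- Keep the telephone call as a second source.
- Classify each reason into fixed categories: reaction after later penicillin exposure; delayed symptoms after the study challenge; re-entered without a new reaction; undetermined.
- Report the number in each category, the number of families not reached, and the cases where record and call disagree.

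The 1-year record review and call should also appear as lines in table 4.d.

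The cost is a few sentences of protocol text and a few minutes of chart review per re-labeled child, in a record already being opened. It adds no visit and changes no treatment. Some reasons may still end as undetermined.
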